#### 8.4.1 Laboratory evaluations

All safety laboratory evaluations will be evaluated locally.

In the case where a laboratory range is not specified by the protocol, but a value is outside the reference range for the laboratory at screening, a decision regarding whether the result is of clinical significance or not shall be made by the Investigator (in consultation with the sponsor as needed) and shall be based, in part, upon the nature and degree of the observed abnormality. If needed, the assessment may be repeated once prior to randomization.

In all cases, the Investigator must document in the source documents, the clinical considerations (i.e., result was/was not clinically significant and/or medically relevant) in allowing or disallowing the participant to continue in the study.

As per [Section 4.6](#), during a Public Health emergency as declared by Local or Regional authorities, i.e., pandemic, epidemic or natural disaster, that limits or prevents on-site study visits, if participants cannot visit the site for protocol-specified safety lab assessments, an alternative local lab collection site may be used.

## Urinalysis

A midstream urine sample (approx. 30 mL) will be obtained, in order to avoid contamination with epithelial cells and sediments, and allow proper assessments.

All abnormal lab results must be evaluated for criteria defining an adverse event and reported as such if the criteria are met. For those lab adverse events, repeated evaluations are mandatory until normalization of the result(s) or until the result is no longer considered to be clinically significant.

Test Category	Test Name
Hematology	Hemoglobin, Platelets, White blood cells, Differential (Basophils, Eosinophils, Lymphocytes, Monocytes, Neutrophils, Other)
Chemistry	Albumin, Alkaline phosphatase, ALT, AST, GGT, Lactate dehydrogenase (LDH), Bicarbonate, Calcium, Chloride, Magnesium, Phosphorus, Sodium, Potassium, Creatinine, Direct Bilirubin, Total Bilirubin, Blood Urea Nitrogen (BUN) or Urea, Uric Acid, Amylase, Lipase, Glucose (non-fasting)
Urinalysis	Macroscopic Panel (Dipstick) (Color, Bilirubin, Blood, Glucose, Ketones, Leukocytes esterase, Nitrite, pH, Protein, Specific Gravity, Urobilinogen)
Pregnancy Test	Serum / Urine pregnancy test (refer to Section 8.4.3 'Pregnancy and assessments of fertility' section)

### 8.4.2 Electrocardiogram (ECG)

ECGs must be recorded after a few minutes rest in the supine or semi-recumbent position to ensure a stable baseline. In addition to any ECGs obtained for clinical care, single time point 12-lead ECG tracings will be captured using the same 12-lead Holter monitor that captures the continuous recording. These safety assessment ECGs should be interpreted by a qualified physician to ensure participant safety. Clinically significant abnormalities must be reported on the AE eCRF.

ECGs to be used in the analyses will be selected by pre-determined time points as defined in [Table 8-1](#) and may be read centrally in addition to local interpretation by the Investigator.

If ECGs are read centrally, the following principals will be followed at the designated CRO:

1. ECG analysts are blinded to the participant, visit and treatment allocation
2. Baseline and on-treatment ECGs for a particular participant will be over-read on the same lead and will be analyzed by the same reader.
3. The primary analysis lead is lead II. If lead II is not analyzable, then primary lead of analysis will be changed to another lead for the entire participant data set.

The Fridericia QT correction formula (QTcF) must be used for clinical decisions.

Unless auto-calculated by the ECG machine, the Investigator must calculate QTcF at the Screening visit (as applicable) to assess eligibility according to the following formula:

$$QTcF = \frac{QT}{\sqrt[3]{RR}}$$

Each ECG tracing must be labeled with study number, participant initials, participant number, date and time, and filed in the study site source documents. Investigator should document clinical evaluation in source. For any ECGs with participant safety concerns, two additional ECGs must be performed to confirm the safety finding. Clinically significant ECG findings that pose a risk to participant safety at Day 1 Time 0 must be discussed with the sponsor before administration of study treatment.

Clinically significant abnormalities must be recorded on the relevant section of the medical history/Current medical conditions/AE eCRF as appropriate.

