### **6.7.2 Instruction for prescribing and taking study treatment**

HSY244 or placebo will be administered to the participant via i.v. injection route of administration for a 15-minute infusion at the study site. Please refer to the Pharmacy Manual for detailed instructions.

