- For Day 1, 90 min: 1) assess injection/infusion site, 2) assess vital signs, 3) short physical exam, 4) blood draw per assessment schedule, 5) obtain ECG tracing, and 6) after confirmation of persistent AF, initiate direct current cardioversion under appropriate sedation/anesthesia, unless deemed inappropriate by the Investigator. Alternatives to medications listed in the prohibited medication list ([Table 6-2](#)) should be used for sedation/anesthesia, as deemed appropriate by the Investigator.
- For Day 1, 180 min: 1) assess injection/infusion site, 2) assess vital signs, 3) short physical exam, 4) blood draw per assessment schedule, 5) obtain ECG tracing, 6) CCI 7) monitor for adverse events. At this point, the participant can leave the study site to return for assessments at the EOS visit. The observation period can be extended through 24 hours if deemed necessary or appropriate by the Investigator and/or for the convenience of the participant.
- For assessments during other Day 1 time points: 1) assess concomitant medications and therapies, 2) assess injection/infusion site reaction, 3) assess vital signs, 4) blood draw per assessment schedule, and 5) monitor for adverse events.

Blood draws should be obtained at the protocol specified time and within the assessment window as specified in [Table 8-1](#). Every effort should be made for the other assessments (e.g., ECG, vital signs, etc.) to be obtained at the specified assessment time either before or after the blood draw, as described by the order of assessments above.

As per [Section 4.6](#), during a Public Health emergency as declared by Local or Regional authorities, i.e., pandemic, epidemic or natural disaster that limits or prevents on-site study visits, alternative methods of providing continuing care may be implemented by the investigator as the situation dictates. If allowable by a local Health Authority and depending on operational capabilities, phone calls, virtual contacts (e.g., tele consult) or visits by site staff/home nursing staff to the participant's home, can replace on-site study visits, for the duration of the disruption until it is safe for the participant to visit the site again.

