**Table 8-1 Assessment Schedule**

Epoch	Screening	Treatment										
Visit Name	Screening 	Day 1								Day 2 	End of Study	Post Study Safety Contact
Visit Numbers 	1	101								102	199	
Days	-3 to 1	1								2	5	Last treatment +30
Time (post-dose)	-	0min	5min	10min	15min ±5 	30min ±5 	60min ±5 	90min ±5 	180min ±5 	24h ±4	96h ±24	-
Informed consent	X											

Commercially Confidential Information

Inclusion / Exclusion criteria	S	S										
Medical history/current medical conditions	X											
Study drug administration		X										
Injection/Infusion site reaction		X	X	X	X	X	X	X	X	X	X	
Demography	X											
Vital Signs	X	X 	X	X	X	X	X	X	X		X	
Body Height	X											
Body Weight	X										X	
Physical Examination	S 	S				S		S	S		S 	

Epoch	Screening	Treatment										
Visit Name	Screening 	Day 1								Day 2 	End of Study	Post Study Safety Contact
Visit Numbers 	1	101								102	199	
Days	-3 to 1	1								2	5	Last treatment +30
Time (post-dose)	-	0min	5min	10min	15min ±5 	30min ±5 	60min ±5 	90min ±5 	180min ±5 	24h ±4	96h ±24	-
Hepatitis screen	S											
HIV screen	S											
Alcohol Test and Drug Screen	S											
Pregnancy and assessments of fertility 	S 										S 	
Hematology	X	X 									X	
Clinical Chemistry	X	X 									X	
Urinalysis	X										X	
PK blood collection		X 			X 	X	X	X	X		X	
Electrocardiogram (ECG)	X	X 				X		X	X		X	
Continuous digital 12-lead Holter		X 										

Commercially Confidential Information

Epoch	Screening	Treatment										Post Study Safety Contact
Visit Name	Screening 	Day 1								Day 2 	End of Study	
Visit Numbers 	1	101								102	199	
Days	-3 to 1	1								2	5	Last treatment +30
Time (post-dose)	-	0min	5min	10min	15min ±5 	30min ±5 	60min ±5 	90min ±5 	180min ±5 	24h ±4	96h ±24	-

Commercially Confidential Information

Adverse Events												X	
Concomitant medications												X	
Concomitant therapies												X	

Commercially Confidential Information

Study completion information													X	
Safety Follow up Call														S

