## **9 Study discontinuation and completion**

### **9.1 Discontinuation and completion**

#### **9.1.1 Study treatment discontinuation and study discontinuation**

The Investigator must discontinue study treatment for a given participant if, he/she believes that continuation would negatively impact the participant's well-being.

Study drug administration must be discontinued under the following circumstances:

- Participant withdraws consent
- Development of new complete bundle branch block (QRS duration >120ms) for a participant with a normal QRS duration at baseline as determined by the Investigator's interpretation of the ECG findings or an increase in QRS duration that in the opinion of the Investigator may be a risk to participant safety
- QTcF >500 ms for those individuals with a normal QTcF at baseline as determined by the Investigator's interpretation of the ECG findings, or an increase in QTcF that in the opinion of the Investigator may be a risk to participant safety
- A change in atrioventricular conduction that in the opinion of the Investigator may be a risk to participant safety
- An increase in the resting heart rate to >130 beats per minute sustained for >2 minutes as determined by the Investigator, unless there is an obvious alternative explanation other than administration of study drug
- Hypotension, defined as >20 mmHg systolic blood pressure drop (repeat measurement) that is (a) symptomatic or (b) sustained to the point requiring medical intervention
- Any moderate or higher CNS-related AE that in the opinion of the Investigator is suspected to be related to the study drug
- A seizure
- A severe or serious adverse event
- Hypersensitivity reactions and/or injection site reactions of moderate severity or greater

If discontinuation of study drug administration occurs, the investigator should make a reasonable effort to understand the primary reason for the participant's premature discontinuation of study drug administration and record this information.

Participants who discontinue study drug administration or who decide they do not wish to participate in the study further should NOT be considered withdrawn from the study UNLESS they withdraw their consent (see 'Withdrawal of Informed Consent' [Section 9.2](#)).

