7.2 Descriptive analyses

Participant demographics and other baseline characteristics

Demographic and other baseline data including disease characteristics will be listed and summarized descriptively by treatment group and cohort for the safety analysis set.

Categorical data will be presented as frequencies and percentages. For continuous data, mean, standard deviation, median, minimum, and maximum will be presented.

Relevant medical histories and current medical conditions at baseline will be summarized by system organ class and preferred term by treatment group and cohort. For AF disease history, if the start month is missing, then the start month will be imputed as 'JAN'. Similarly, if the start day is missing, the start day will be imputed as '01'.

Treatment

Data for study drug administration (rescue medication), concomitant medications and significant non-drug therapies prior to and after the start of the study treatment will be listed and summarized according to the Anatomical Therapeutic Chemical (ATC) classification system by treatment group and cohort.

Vital signs

All vital signs data will be listed by treatment group, cohort, participant, and visit/time and if ranges are available, abnormalities (and relevant orthostatic changes) will be flagged. Summary statistics will be provided by treatment, cohort and visit/time.

ECG evaluations

- 1. PR, QRS, QT, QTcF, and RR intervals will be obtained from single time point ECGs for each participant during the study. ECG data will be read and interpreted locally for initial safety readouts. The single time point ECGs will be read centrally for the parameters above and these will be reported in the CSR.
- 2. Categorical Analysis of QT/QTcF interval data based on the number of participants meeting or exceeding predefined limits in terms of absolute QT intervals or changes from baseline will be presented. In addition, a listing of these participants will be produced (by treatment group).

QT/QTcF and QRS duration will be examined separately between individuals with and without a complete bundle branch block.

All ECG data will be listed by treatment group, cohort, participant, and visit/time, and abnormalities will be flagged.

Summary statistics will be provided by treatment, cohort and visit/time.

Commercially Confidential Information

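### As visibly written, the QT outlier count rests on scheduled ECGs only, so a limit exceeded only on an unscheduled or repeat tracing would not be counted

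*Protocol*

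**What the plan says.** **Selection of ECGs.** Protocol 8.4.2 states that "ECGs to be used in the analyses will be selected by pre-determined time points as defined in" Table 8-1, and adds that they may be read centrally. The same section treats the single time point tracings from the Holter device as separate from ECGs done for clinical care. It also requires repeats: "For any ECGs with participant safety concerns, two additional ECGs must be performed to confirm the safety finding".

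**Schedule.** The ECG row of Table 8-1 marks screening, pre-dose, 30, 90 and 180 minutes, and the end-of-study visit at 96 hours. For the remaining Day 1 times, protocol section 8 gives this order: "For assessments during other Day 1 time points: 1) assess concomitant medications and therapies, 2) assess injection/infusion site reaction, 3) assess vital signs", followed by the blood draw and adverse event monitoring. No ECG tracing is in that list.

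**Infusion and discontinuation.** Protocol 6.7.2: "HSY244 or placebo will be administered to the participant via i.v. injection route of administration for a 15-minute infusion at the study site". Among the reasons in 9.1.1 for stopping administration is "QTcF >500 ms for those individuals with a normal QTcF at baseline as determined by the Investigator's interpretation of the ECG findings".

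**Analysis.** SAP 7.1 uses central-reader values derived from the single time point ECG data. SAP 7.2 plans a "Categorical Analysis of QT/QTcF interval data based on the number of participants meeting or exceeding predefined limits", with a listing of those participants; protocol 12.5.1 plans the same. Both documents also list all ECG data with abnormalities flagged, and 8.4.2 sends clinically significant abnormalities to the adverse event form.

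**The concern.** One selection rule appears to serve two kinds of analysis. Summaries by time need fixed times, so that every participant contributes comparably. A participant-level count of exceedances is an ever/never question, and leaving out tracings can only lower that count or leave it unchanged. Unscheduled tracings are usually taken because something looked wrong, so they are the ones most likely to hold an exceedance.

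The protocol does use a worst-value rule elsewhere: its laboratory shift tables in 12.5.1 compare baseline with the worst value on treatment. No equivalent is visible for QT.

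The stake is the drug's rationale. The protocol summary and section 1.1 expect conversion to sinus rhythm with little or no effect on ventricular repolarization, and the outlier table is a direct check on that. A participant stopped during the infusion is also outside the primary analysis, which is limited to those who complete treatment (protocol 12.4.2, SAP 6.1.3). The safety tables then carry most of what is learned from that participant.

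**Working it through.** The documents give no expected rate, limit or sample size for QT outliers, so there is no figure of the plan's own to reproduce. The check compares the passages and then gives a sense of scale.

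**Step 1: timing.** Post-dose ECGs are scheduled at 30, 90, 180 and 96 × 60 = 5,760 minutes after the start of infusion. The infusion runs from 0 to 15 minutes. No scheduled ECG falls in that window, yet the QTcF discontinuation criterion in 9.1.1 operates there.

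**Step 2: which cases the literal rule misses.**

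| Where the limit is exceeded | Scheduled tracings only | All post-dose tracings |
|---|---|---|
| A scheduled ECG, on the central read | Counted | Counted; repeats add nothing |
| An unscheduled tracing, and also a scheduled one | Counted | Counted |
| An unscheduled tracing only | Not counted | Counted |
| A repeat only, because the scheduled index ECG is below the limit on the central read | Not counted | Counted |

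The loss is confined to the last two rows. Confirmatory ECGs therefore matter only when the index ECG is off-schedule or does not itself exceed the limit on the central read.

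**Step 3: size if one participant is affected.** Input: about 20 participants on HSY244 in Cohort 1 (protocol section 3). Exact (Clopper-Pearson) 95% limits:

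- 0/20: upper limit = 1 − 0.025^(1/20) = 16.8%.
- 1/20 = 5.0%: lower limit = 1 − 0.975^(1/20) = 0.1%; upper limit solves (1 − p)^20 + 20p(1 − p)^19 = 0.025, giving 24.9%.

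The stated 5:1 ratio applied to 29 randomized gives 29 × 5/6 = 24.2. With 24 treated, the comparison is 0/24 (upper limit 14.2%) against 1/24 (4.2%, 0.1% to 21.1%).

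**Step 4: how often this could happen.** Let p be the true probability that a participant exceeds a limit only off-schedule. The documents do not give p, so it is assumed. The chance that at least one of 20 is missed is 1 − (1 − p)^20:

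| Assumed p | Chance of at least one missed |
|---|---|
| 1% | 18% |
| 2% | 33% |
| 5% | 64% |
| 10% | 88% |

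**Step 5: would the 30-minute ECG catch it anyway?** That depends on how long an effect lasts, which the visible text does not give. As one assumed scenario, take a rise of 80 ms at minute 12 and a limit of more than 60 ms change. The rise remaining at 30 minutes is 80 × 0.5^(18/h) for an effect half-life of h minutes. For h = 10 it is 23 ms and for h = 30 it is 53 ms, both below the limit. The limit is exceeded once 0.5^(18/h) > 60/80, that is h > 18 × ln 2 / ln(4/3), about 43 minutes. The scheduled ECG could therefore miss or catch the event.

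**The case against.** The strongest reply is that the exclusion is inferred. The sentence in 8.4.2 does not contain the word only, and it leads into the rules for central reading. The passages that define the categorical analysis place no time-point restriction on it. A repeat tracing taken on the Holter device could fit the SAP's description of single time point data. Part of the SAP's ECG text is blacked out, so a handling rule may exist there. All of this stands as a limit on certainty, which is why the point is about the plan as visibly written. It does not remove the problem: 8.4.2 states a selection rule, and no visible text lifts it for the outlier count.

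A reader might infer several stronger claims that the documents do not support:

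- *That all mandatory confirmatory ECGs are lost from the count.* They change nothing when a scheduled index ECG already exceeds the limit on the central read.
- *That every stop under the QTcF criterion rests on a discarded tracing.* Section 3 provides for bedside telemetry and continuous 12-lead recording during the infusion, so an investigator could act on those without a separate tracing.
- *That the event disappears from the report.* It should be in the full ECG listing and, if clinically significant, among the adverse events; 9.1.1 also has the discontinuation reason recorded.
- *That 500 ms is an outlier limit.* It is visible only as a discontinuation criterion; the categorical limits are not visible.
- *That a bias toward no QT effect has been shown.* The possible error runs in one direction, but its size is unknown. The SAP also plans repeated-measures and concentration-effect analyses of ECG data, which do not depend on this count.

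The reply also notes that a worst-value rule favours finding exceedances in participants with more tracings, and that local readings depart from the central-reader rule. Both are fair and are addressed in the fix.

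**Conclusion.** The concern holds in limited form. On the visible text, a participant whose QT or QTcF exceeds a categorical limit only on an off-schedule or repeat tracing is left out of the outlier table and its listing. The schedule makes this a practical gap, because no ECG is planned during the infusion. Visibility in other listings does not correct the count.

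The magnitude is illustrative: one affected participant among about 20 is the difference between 5.0% and 0%, and the two exact intervals overlap heavily. The conclusion rests on a literal reading of 8.4.2 and SAP 7.1, and on no contrary rule sitting in the blacked-out text. It does not rest on any assumed time course of QTcF. It merits a correction to the SAP because, with so few treated, one participant determines what the table shows, and its content should not be left to a programming choice.

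**What to change.** In protocol 8.4.2 and SAP 7.2:

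- Keep the Table 8-1 time points for summaries by time.
- For the categorical QT/QTcF analysis and its listing, count each participant on the worst 12-lead value after time 0 (the start of infusion), including unscheduled and repeat tracings.
- Read these tracings centrally from the 24-hour Holter record where it covers the time. Otherwise use the local value and flag it.
- Show the scheduled-only count beside it.

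The cost is a short addition to the text and a few extra central readings from a recording that already exists. No new procedure or clinical rule is needed. There are two downsides: participants with more tracings have more chances to cross a limit by noise, and flagged local values depart from the SAP's central-reader rule. Showing both counts, with local values flagged, lets the reader see how far either matters.

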### **8.4.3 Pregnancy and assessments of fertility**

A condom is required for all sexually active male participants to prevent them from fathering a child AND to prevent delivery of study treatment via seminal fluid to their partner. In addition, male participants should not donate sperm for 96 hours after study drug administration.

#### **Pregnancy Test**

All pre-menopausal women who are not surgically sterile will have pregnancy testing. Additional pregnancy testing might be performed if requested by local requirements.

If participants cannot visit the site to have local serum pregnancy tests during a Public Health emergency as declared by Local or Regional authorities, i.e., pandemic, epidemic or natural disaster, that limits or prevents on-site study visits, urine pregnancy test kits may be used, if and where permitted by the local regulations and agreed with the local Health Authorities (in Germany only serum pregnancy tests are permitted at screening and EOS visits). Relevant participants can perform the urine pregnancy test at home and report the result to the site. A communication process should be established with the participant so that the site is informed and can verify the pregnancy test result (e.g., following country specific measures).

